### 9.1 Extent of Exposure

In Stage 1, subjects randomized to OPC-167832 will receive once daily oral doses of IMP (OPC-167832) from Day 1 through Day 14. After Day 14, the subjects will receive treatment for pulmonary TB according to the local standard of care regimen (RHEZ). In subjects with no clinical indication to start RHEZ immediately, commencement of RHEZ can be delayed for up to 3 days (Days 15, 16, and 17) under close supervision in the trial site hospital ward. Subjects randomized to RHEZ will receive once daily oral doses of RHEZ from Day 1 through Day 20.

In Stage 2, subjects randomized to IMP (OPC-167832 and/or delamanid and/or BDQ) will receive once daily oral doses of IMP from Day 1 through Day 14. After Day 14, the subjects will receive treatment for pulmonary TB according to the local standard of care regimen (RHEZ). In subjects with no clinical indication to start RHEZ immediately, commencement of RHEZ can be delayed for up to 3 days (Days 15, 16, and 17) under close supervision in the trial site hospital ward. Subjects randomized to RHEZ will receive once daily oral doses of RHEZ from Day 1 through Day 20.

Exposure to IMP is considered to be the exposure of OPC, DLM or BDQ (for the three OPC-containing regimens) in study days 1-14. For comparison purposes, for the RHEZ arm also, exposure to IMP will be taken to be the exposure to any treatment with RHEZ in days 1-14, and will be tabulated for the first 14 days only. The total exposure to IMP or reference product (RHEZ) in days will be divided to time intervals (No exposure, 1-2 days, 3-4 days, etc.) and the number and percentage of patients whose durations of exposure are in each interval will be presented for each treatment group. The duration of exposure is calculated as the last date of IMP (within 14 study days) – first date of IMP +1. For patients who are lost to follow-up, the last known date of taking IMP or RHEZ (within 14 study days) will be used for missing last date.

Patients randomized to RHEZ will receive once daily oral doses of RHEZ from Day 1

through Day 20. For the RHEZ group, the exposure table will summarize the exposure to RHEZ within the first 14 days of treatment only

All analyses will be presented by treatment groups for Stage 1, and Stage 2 with a combined RHEZ group from Stage 1 and Stage 2.

The summaries will be based on the Randomized Analysis Set. IMP dosing will be listed. The dosing of RHEZ will be listed in the anti-TB concomitant medication listing.

#### 9.2 Adverse Events

All AEs will be coded by Medical Dictionary for Regulatory Activities (MedDRA; Version 22 or newest available) system organ class and preferred term. Treatment-emergent AEs (TEAE) are defined as AEs that occurs after the initiation of trial treatment; or an event or pre-existing medical problem that has changed adversely in nature or severity from baseline in a subject while receiving trial treatment. The frequency and percentage of subjects with the following events will be summarized by SOC, MedDRA preferred term, severity and treatment:

- Treatment-emergent AEs (TEAEs)
- TEAEs potentially causally related to the IMP or RHEZ
- TEAEs with an outcome of death
- Serious TEAEs
- TEAEs leading to discontinuations of the IMP
- TEAEs by DAIDS grading
- non-serious TEAEs (NSAE)

All AEs will be presented in a listing. The listing of death due to AE, serious AE and TEAE leading to discontinuation will also be provided. In addition, the number and frequency of TEAE incidences will be summarized for serious TEAE, serious study medication related TEAE and non-serious TEAE. The analyses on AEs will be performed separately for Stage 1, and Stage 2 with a combined RHEZ group from Stage 1 and Stage 2.

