	Day -6 to Day -3 a	Day -2 b	Day -1	Day 1	Day 2	Day 3	Day 4	Days 5 and 6	Day 7	Days 8 through 13	Day 14	Day 15	Days 16 through 19	Day 20/ET	14 (± 3) Days c	
PK blood samples for OPC-167832 only (stage 1) or OPC-167832, delamanid, DM-6705, and BDQ (stage 2) †				X	X						X (Days 12 and 13 only)	X	X	X	X	
PK blood samples rifampicin, and isoniazid (stages 1 and 2) ‡											X				(X)	
Overnight sputum collection v		X	X		X		X	X (Day 6 only)		X (Days 8, 10, and 12 only)	X					
Meals w		X	X	X	X	X	X	X	X	X	X	X	X	X	X	X
Discharge from trial site															X	
Assess AEs x	X	X	X	X	X	X	X	X	X	X	X	X	X	X	X	X
Record prior/concomitant medications y	X	X	X	X	X	X	X	X	X	X	X	X	X	X	X	X
Telephone contact																X

Note: This table presents the trial assessment time points and should be used in conjunction with the Trial Days and Activities table (Table 3.7.3-1), which summarizes the timing of assessments and activities by trial period/trial day.

BMI = body mass index; FSH = follicle-stimulating hormone.

aScreening can be extended up to 7 days (Day -9 to Day -3), if needed.

bSubjects can begin with the Day -2 assessments as soon as all their screening assessments have been completed.

Protocol 323-201-00003

cFollow-up: 14 ( $\pm$  3) days after the last dose of trial treatment. Trial treatment is defined as IMP or RHEZ, received on Days 1 to 14.

dHeight will only be measured at screening.

eComplete physical examinations will be performed at screening and on Day -1. Targeted physical examinations will be performed on Days 1 through 14 (predose and 4 hours postdose) and Days 15 through 20 or at ET. A targeted physical examination should include at a minimum a general assessment and examination of the cardiac and respiratory systems (additional systems may be assessed as clinically indicated). The 4-hour post-dose targeted physical examination could be performed  $\pm$  30 minutes after the expected post-dose timepoint.

fIf a chest x-ray is available that has been taken within 2 weeks prior to screening, which in the opinion of the investigator is a reflection of the subject's TB status, is of adequate quality, and which can be kept with the trial documentation for the required duration, this x-ray can be used as the screening x-ray.

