## 5.2 Eliciting and Reporting Adverse Events

The investigator will assess subjects for the occurrence of AEs from the time the ICF is signed until the end of the trial. For this trial, information on AEs will be followed for up to 14 ( $\pm 3$ ) days after the last dose of trial treatment (IMP or RHEZ) has been administered. To avoid bias in eliciting AEs, subjects should be asked the following nonleading question: “How are you feeling?” All AEs (serious and nonserious) reported by the subject must be recorded on the source documents and eCRFs provided by the sponsor. Serious AE collection is to begin after a subject has signed the ICF.

Use medical terminology in AE reporting. Adverse events should be reported as a single unifying diagnosis whenever possible or, in the absence of a unifying diagnosis, as individual signs or symptoms. Exacerbation or disease progression should be reported as AEs only if there are unusual or severe clinical features that were not present, not experienced earlier, or not expected based on the course of the condition.

In addition, the sponsor and Clindev Pty Ltd must be notified immediately by fax or e-mail of any IREs according to the procedure outlined below in [Section 5.3](#). Special attention should be paid to recording hospitalization and concomitant medications.

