#### **7.6.1 Adverse Events**

All AEs will be coded by MedDRA system organ class and preferred term. The incidence of the following events will be summarized by treatment:

- TEAEs
- TEAEs by severity
- TEAEs potentially causally related to the IMP or RHEZ
- TEAEs with an outcome of death
- Serious TEAEs
- TEAEs leading to discontinuation of the IMP or RHEZ
- TEAEs by DAIDS grading

Treatment-emergent AEs are defined as AEs that occur after the initiation of trial treatment; or an event or pre-existing medical problem that has changed adversely in nature or severity from baseline in a subject while receiving trial treatment.

Adverse event data will be presented in listings.

Protocol 323-201-00003

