- No more than 2 subjects with Grade 4/5 AEs ("Division of AIDS [DAIDS] Table for Grading the Severity of Adult and Pediatric AEs") assessed as related to OPC 167832.

# 3.1.2 Stage 2

The dose of OPC-167832 for Stage 2 has been determined based on the safety, tolerability, PK and efficacy data from Stage 1 of this trial. Based on the Stage 1 PK/PD analysis of OPC-167832 plasma concentrations and reduction in log10CFU/mL, a dose lower than the current 30 mg specified in the protocol may be considered, provided it can offer similar potential for efficacy as the 30 mg dose.

Stage 2 will be a randomized, open-label, active-controlled, parallel group comparison stage comprising of 46 subjects (subjects who were randomized in stage 1 cannot enroll in stage 2).

Subjects who signed ICF will be admitted to the trial site at screening. Subjects will be screened for 4-7 days prior to the start of Day -2 assessments. Eligible subjects will be housed at the trial site until discharge or early termination. All subjects enrolled during this stage of the trial will be randomized prior to first dosing on Day 1 to one of the following 4 treatments in a ratio of 14:14:14:4:

- 30 mg OPC-167832 and 300 mg delamanid QD (14 subjects)
- 30 mg OPC-167832 and 400 mg BDQ QD (14 subjects)
- 30 mg OPC-167832 and 300 mg delamanid and 400 mg BDQ QD (14 subjects)

• RHEZ QD (4 subjects)

Subjects receiving BDQ will take a loading dose of 700 mg BDQ on Day 1 and 500 mg on Day 2. The dose of BDQ will be 400 mg QD for days 3 to 14.

Subjects will be centrally randomized through an interactive voice response system with no stratification.

Subjects randomized to OPC-167832 and/or delamanid and/or BDQ will receive QD oral doses of IMP (OPC-167832 and/or delamanid and/or BDQ) from Day 1 through Day 14. After Day 14, the subjects will receive treatment for pulmonary TB according to the local standard of care regimen (RHEZ). In subjects with no clinical indication to start RHEZ immediately, commencement of RHEZ can be delayed for up to 3 days (Days 15, 16, and 17) under close supervision in the trial site hospital ward.

Subjects randomized to RHEZ will receive QD oral doses of RHEZ from Day 1 through Day 20.

Subjects will be discharged on Day 20 once all safety assessments have been completed and all PK samples have been collected.

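### TEAEs are counted to about Day 28 by randomized arm although IMP-arm subjects take RHEZ from Days 15 to 18, which dilutes the safety comparison with RHEZ; summaries by onset period are needed

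*SAP*

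**What the plan says.** **Definition.** In SAP 9.2, treatment-emergent AEs "are defined as AEs that occurs after the initiation of trial treatment"; protocol 7.6.1 has "Treatment-emergent AEs are defined as AEs that occur after the initiation of trial treatment". Both add a second limb for existing problems that worsen while the subject is receiving trial treatment. That phrase limits only the second limb; the first has no end.

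**Collection.** Protocol 5.2: "The investigator will assess subjects for the occurrence of AEs from the time the ICF is signed until the end of the trial". The same section says that "information on AEs will be followed for up to 14" (±3) days after the last dose of trial treatment. Table 3.7-1, footnote c, sets that clock: "Trial treatment is defined as IMP or RHEZ, received on Days 1 to 14".

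**Switch.** IMP ends on Day 14 and standard-of-care RHEZ follows. SAP 9.1 allows that "commencement of RHEZ can be delayed for up to 3 days (Days 15, 16, and 17"), and protocol Table 3.7.3-1 has all subjects on RHEZ on Day 18. The RHEZ arm stays on RHEZ through Day 20 and is then referred for continued standard treatment.

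**Attribution.** SAP 9 summarizes safety by randomized treatment. One SAP 9.2 table pools TEAEs related to IMP or to RHEZ.

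**Windows used elsewhere.** For exposure in the RHEZ arm, SAP 9.1 says "exposure to IMP will be taken to be the exposure to any treatment with RHEZ in days 1-14". SAP 7.5 defines a treatment period ending at the last IMP dose, or Day 14 for RHEZ, and uses it for concomitant medication. Neither rule is carried into 9.2 (AEs) or 9.3 (laboratory data).

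**The concern.** Safety and tolerability compared with RHEZ is a primary objective in both stages (SAP 2.1). In the second part of the TEAE window, subjects in every arm are on the same regimen, the comparator. Events that begin then say little about IMP against RHEZ, yet they enter the same table under the randomized arm. A real difference during Days 1 to 14 is mixed with a shared period and looks smaller. The loss can go either way: a safety advantage of OPC-167832 or an excess of harm could be masked. Exposure is shown over 14 days and AEs over about 28, so the two tables do not describe the same period. The pooled relatedness table does not help, because a post-switch event judged related to RHEZ can appear as related under an OPC-167832 arm.

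**Working it through.** **1. Last day of the window.** Protocol 3.7 gives about 34 days of participation per subject. Days -6 to -1 are 6 days, Days 1 to 14 are 14, and follow-up is 14: 6 + 14 + 14 = 34, which reproduces the stated figure. Counting follow-up from Day 20 gives 6 + 20 + 14 = 40, which does not. Collection therefore ends at Day 14 + 14 = 28, or 25 to 31 with the ±3 days.

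**2. Share of the window on RHEZ in the IMP arms.** With RHEZ starting on day S and the window ending on day E, the share is (E - S + 1)/E.

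| E | S = 15 | S = 18 |
|---|---|---|
| 25 | 11/25 = 44% | 8/25 = 32% |
| 28 | 14/28 = 50% | 11/28 = 39% |
| 31 | 17/31 = 55% | 14/31 = 45% |

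This assumes that RHEZ continues after discharge, which is by referral and not observed dosing.

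**3. How those days are observed.** In the 20 inpatient treatment days, RHEZ covers Days 15 to 20 (6/20 = 30%) or Days 18 to 20 (3/20 = 15%). After Day 20, AEs come from one telephone contact.

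**4. Laboratory data.** Protocol draws after baseline are on Days 4, 7, 14 (all predose) and 20. In continuing subjects one of the four, Day 20, follows the switch, after 3 to 6 days of RHEZ.

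**5. Effect on the contrast (illustration).** Let p and q be 14-day risks on IMP and on RHEZ. Both are assumptions; the documents give none. Take a constant hazard, no events on RHEZ-free days, and d days on RHEZ to Day 28 (14 or 11).

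- IMP arm: 1 - (1 - p)(1 - q)^(d/14)
- RHEZ arm: 1 - (1 - q)^2

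For p = 10%, q = 30%:

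- Days 1 to 14: 10% vs 30%, RR 0.33, difference -20 points.
- RHEZ arm to Day 28: 1 - 0.7^2 = 51%.
- IMP arm, RHEZ from Day 15: 1 - 0.9 × 0.7 = 37%; RR 0.73, difference -14 points.
- IMP arm, RHEZ from Day 18: 1 - 0.9 × 0.7^(11/14) = 32%; RR 0.63, difference -19 points.
- In an IMP arm of 14, expected subjects with the event go from 1.4 to between 4.5 and 5.2.

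For p = 50%, q = 20% (IMP worse), RR 2.50 becomes 1.67 (60% vs 36%) with a Day 15 start and 1.61 (58% vs 36%) with a Day 18 start.

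With a Day 15 start the difference is exactly (1 - q)(p - q), so it shrinks by the factor 1 - q. With a Day 18 start the ratio still moves toward 1, but the difference may hardly change: for p = 5%, q = 20% it goes from -15.0 to -15.7 points while RR goes from 0.25 to 0.56.

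**The case against.** The strongest reply is that counting follow-up events as TEAEs is a common conservative choice, stated identically in protocol and SAP, in a trial whose comparisons are descriptive and unpowered (SAP 4). Several parts of the case against stand:

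- **No one-sided bias.** A reader might infer that post-switch events are held against OPC-167832 alone. The documents do not support that: the RHEZ arm is counted over the same days. Setting the IMP arm's 32 to 37% beside the RHEZ arm's 14-day figure of 30% would mislead; the matching figure is 51%.
- **Not unlimited.** The definition has no end, but collection stops at about Day 28.
- **Days are not equal.** The 39 to 50% share includes telephone-only follow-up; of the inpatient days it is 15 to 30%.
- **Laboratory data are less affected.** Only one of four post-baseline draws follows the switch. SAP 9.3 does not say whether abnormality and shift tables are by visit; if they are, Day 20 is already separate.
- **Dose decisions are not exposed in the same way.** The escalation criteria in protocol 3.1.1 use deaths and Grade 4/5 events assessed as related to OPC-167832. TEAEs leading to IMP discontinuation are also largely outside the problem, since IMP ends on Day 14.
- **A hard cut at Day 14 would be wrong.** It would drop the RHEZ-free days and late IMP effects. Protocol 1.3 gives terminal half-lives of about 5.5 months for BDQ and M2 and about 230 hours for DM-6705, the metabolite most closely linked to QT prolongation.

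What the reply does not answer is that no summary in the readable text separates the two periods. Subject listings would allow a reader to do so by hand, but a primary safety comparison should not depend on that.

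**Conclusion.** The point holds as a matter of interpretation. Applied exactly, the stated rule tabulates 11 to 14 of about 28 days (39 to 50%; 32 to 55% over the follow-up limits) under the IMP arms while those subjects take the comparator. The result is mainly dilution of the contrast with RHEZ, in either direction; the ratio is affected more consistently than the difference. Type I error and power are not at issue, because no test is planned. The window lengths follow from the documents. The risk figures are illustrative and rest on assumed risks, a constant hazard and continued RHEZ after discharge. One reservation remains: SAP Appendices 6 and 7 (technical details and table list) are not shown, so a by-period table there cannot be excluded. If one exists, the remaining change is to state the periods in the text of 9.2 and 9.3.

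**What to change.** Keep the all-period TEAE table. Add to SAP 9.2 and 9.3 summaries of TEAEs and laboratory abnormalities by onset period:

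- **(a) Before the switch:** from first dose to last IMP dose, plus the RHEZ-free days before the first standard-of-care RHEZ dose. These may be shown as two periods, which lets Days 1 to 14 line up directly across arms.
- **(b) After the switch:** from the first standard-of-care RHEZ dose to the end of follow-up.
- **RHEZ arm:** matching day split, Days 1 to 14 and after.
- **Laboratory:** Day 20 results shown in the post-switch period.
- **Relatedness:** to IMP and to RHEZ tabulated separately where recorded. Protocol 5.1 describes a single assessment against either, so this may not always be possible.

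State how an event with onset on the day of the first RHEZ dose is assigned.

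The cost is one extra set of tables. AE onset is needed for the TEAE rule anyway, and SAP 9.1 already lists RHEZ dosing with anti-TB concomitant medication. Trial conduct does not change. The drawbacks are small counts per period and that late effects of long half-life drugs may fall in period (b), which is why the all-period table should stay.

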## 9.3 Clinical Laboratory Data

Clinical hematology, chemistry, coagulation and urinalysis are tested at screening, Day 1, Day 4, Day 7, Day 14 and Day 20/ET for both Stage 1 and Stage 2.

For clinical laboratory tests data, baseline is defined as the last non-missing value obtained on or before Day -1.

The incidence of clinical laboratory test abnormalities, as defined in the "Division of AIDS (DAIDS) Table for Grading the Severity of Adult and Pediatric Adverse Events will be summarized by grade and treatment group and listed by test. The DAIDS criteria for laboratory test results are listed in Appendix 1.

Shift tables assessing status (low, normal, or high based on the clinical laboratory normal ranges) changes from baseline will be presented by treatment group based on the Safety Analysis Set. All cases of lab results where ALT (alanine aminotransferase) or AST (aspartate aminotransferase) are  $\geq 3$  times the normal upper limit and at the same time the total bilirubin is  $\geq 2$  times normal upper limit. All clinical laboratory test data will be listed.

In case of a repeated lab test, the last repeat test on the same visit will be used for the value at that visit. Unscheduled lab test data will not be included in the mean change from baseline summary but will be included when searching for laboratory test abnormalities in the incidence and shift analyses.

When lab parameter values are recorded as < or > a cutoff value, then the lab value is set as 50% of the cutoff value in the case of < and 150% in the case of > when used as a continuous variable. In data listing the originally collected format will be presented.

All analyses will be presented by treatment groups for Stage 1, and Stage 2 with a combined RHEZ group from Stage 1 and Stage 2.

### 9.4 Vital Sign Data

Vital signs (blood pressure, heart rate, temperature, and respiratory rate) will be assessed at screening and on Day -1, Day 1 (predose and at 1, 2, 4, 8, and 12 hours postdose), Days 2 through 6 (predose and 2 and 4 hours postdose), Day 7 (predose and 1, 2, 4, 8, and 12 hours postdose), Days 8 through 13 (predose and 2 and 4 hours postdose), Day 14 (predose and 1, 2, 4, 8, and 12 hours postdose), and Days 15 through 20 or at ET. At screening, blood pressure and heart rate will be taken with the subject in the supine (performed first) and sitting position after remaining for  $\geq$  3 minutes in each position and temperature and respiratory rate will be taken with the subject in the supine position for at least 1 minute. At all other time points, vital signs will be obtained after the subject has been at rest in the supine position for 1 to 3 minutes. Vital signs will be obtained prior to the ECG and PK blood draw at the nominal time points, where applicable. The post-dose

vital signs could be performed within 15 minutes earlier than the expected post-dose timepoints.

The baseline of vital sign is defined as data collected at Day 1 predose. If Day 1 predose is missing, then baseline can be taken from Day -1 or screening.

Change from baseline in vital signs will be summarized for each post-baseline timepoints. The "last visit" in the summaries includes last observed non-missing data collected at post-baseline visits. The incidence of vital signsas based on the tablein Appendix 2, specifying potentially clinically relevant abnormalities, will be summarized for all visits. Also incidence of vital signs based on the "Division of AIDS (DAIDS) Table for Grading the Severity of Adult and Pediatric Adverse Events" as listed out in Appendix 3 will also be summarized by grade and treatment group and will be listed.

When vital sign is repeated, the last repeat value will be used in the summary for that visit. Unscheduled vital sign data will not be summarized in the change from baseline analysis, but will be included in incidence of clinical relevance analysis.

All analyses will be presented by treatment groups for Stage 1, and Stage 2 with a combined RHEZ group from Stage 1 and Stage 2.

# 9.5 Physical Examination Data

Complete physical examinations will be performed at screening and on Day -1. Targeted physical examinations will be performed on Days 1 through 14 (predose and 4 hours postdose) and Days 15 through 20 or at ET. The 4-hour post-dose targeted physical examination could be performed  $\pm 30$  minutes around the expected post-dose timepoint.

Baseline is defined as Day 1 predose. If Day 1 predose is missing, then Day -1 or screening can be used as baseline.

Frequency of percentage of subjects for each physical examination outcome will be presented by visit and treatment group.

All analyses will be presented by treatment groups for Stage 1 and Stage 2 separately, and with a combined RHEZ group from Stage 1 and Stage 2.

### 9.6 Electrocardiogram Data

Standard 12-lead ECGs will be collected in triplicate (5 minutes apart) at screening and on Day -1, Day 7 (predose), and Day 14 (predose). The ECGs will be recorded after the subject has been supine and at rest for  $\geq 10$  minutes prior to the first ECG and subjects will remain supine through the final ECG. Electrocardiograms will be obtained prior to the PK blood draw and after vital signs at the nominal time points, where applicable.

Heart rate, ventricular rate, RR interval, PR interval, QRS duration, and QT intervals will be recorded. The QTcF and corrected QT interval using Bazett's method (QTcB) will be calculated.

ECGs are available in triplicates at each nominal timepoint, but may appear as a single or duplicate assessment. All (single, duplicate or triplicate) ECGs at each nominal time point will be averaged and the average will be used in descriptive summary statistics and frequency and percentages. Baseline of ECG is defined as the averaged measurement on Day -1. If the measurement from Day -1 is missing, the screening ECG is taken as baseline.

Summary and change from baseline for ECG will be presented for continuous ECG parameters by visit and treatment group.

Incidence and percentage of potentially clinically significant ECG parameters as defined in Appendix 4 will be presented for each treatment group. All post baseline visit till end of study will be included in incidences of significant change or value. For criteria that involves change from baseline, the subject must have a baseline value to be included in the analysis. For absolute criteria the complete Safety Set will be included.

Incidence of potentially clinically significant QT increases will also be summarized by treatment groups.

In summarizing the incidence of abnormalities, a patient must have had an evaluation that met abnormality criteria by the end of trial, i.e. last contact date. Incidence rate is calculated as the number of patients having at least one abnormality within a trial period divided by the number of patients who are both exposed to trial medication and have an on-treatment evaluation within that trial period.

When the ECG is repeated, the last repeat value will be used in the summary for that visit. Unscheduled ECG data will not be summarized in the change from baseline descriptive analysis but will be included in the incidence of clinically relevant table.

All analyses will be presented by treatment groups for Stage 1, and Stage 2 with a combined RHEZ group from Stage 1 and Stage 2.

